- Use a unique mHealth approach with open-source application coding and a future basis for ecological momentary assessment extending beyond commercial devices that are at risk for becoming obsolete;
- Incorporates emerging technology into a comprehensive care model in obesity care;
- Create collaborations with mHealth technologists and telehealth experts allowing for translation of innovative laboratory-based technologies into practical applications for medically complex populations in rural settings;
- Use mixed-methods to identify factors leading to behavioral change using technology in the study population;
- Apply lessons learned from this study to other disadvantaged, low-income disparity populations.

APPROACH

Study Design: A single-arm, mixed-methods study that will adopt a pragmatic delivery approach to: a) assess the intervention's feasibility/acceptability; b) investigate the potential effectiveness; and c) ascertain outcomes of implementation. We will recruit 30 obese patients from the D-H Weight & Wellness Center (DH-WWC) to participate in a 12-week pilot that includes monthly assessments and qualitative semi-structured interviews.

Study Site: D-H, in Lebanon, NH, serves 1.5 million persons in New Hampshire and Vermont. Demographics mirror a typical rural New England town (95.4% Caucasian⁵⁶). The DH-WWC is a specialty referral-based obesity clinic whose aim is to improve the health and wellness of patients with obesity. The clinic uses the Epic electronic health record (EHR), and has rooms for interviews, assessments, and video-conferencing.

Selection Criteria: For the purposes of this pilot, we limited inclusion criteria to: community-dwelling, English-speaking patients (age 18-65 years; BMI $\geq 30\text{kg}/\text{m}^2$) with home Wi-Fi high-speed Internet and clearance from their clinician. Patients with dementia (lacking consent), bariatric surgery, severe mental or life-threatening illness, substance use, or exercise contraindications⁵⁷ are excluded as these criteria interfere with the possible efficacy of the intervention. Future pragmatic trials will relax the criteria to allow a pragmatic interpretation.

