e) **Remote Monitoring:** The *Amulet* is an mHealth wrist-worn device with remote sensing and self-monitoring capabilities, functioning independently of a smartphone (battery life lasts >9 days). A 9-axis gyroscope, accelerometer, magnetometer and sensor captures motion, activity type, exercise, and speed data. As part of [name] K23, *Amulet* applications were developed to measure steps, strength, and activity (sedentary, walking, running). Two-way data transfer occurs via a micro-SD card, or low-energy Bluetooth 4.0 to a secure cloud-based repository that is accessible to the team. Predetermined one-line automated scripts (if goals are not met), prompts, and asynchronous messaging can be sent by staff. Programmable reminders (blinking lights, text, haptic buzzer) and audio-visual feedback allow the *Amulet* to celebrate goal attainment.

Outcomes Measures: These were chosen based on their validity, brevity and presence within the HER:

Table 1: Study Variables and Objective Outcome Measures

Aim 1: Feasibility and acceptability of an eHealth-delivered health coaching obesity intervention						Timepoint			
Domain	Outcome/Co-Variate	Instrument	Adm	Length	Source	0	1	2	3
Feasibility	Recruitment/Retention	Eligibility, enrollment, dropout data	RA	---	Study Log	✓	✓	✓	✓
	Engagement/Assessments	>80% attend + complete sessions	RA	---	Study Log	✓	✓	✓	✓
Acceptability	Satisfaction of Intervention	Semi-structured interview	RA	30 min	Participant			✓	
	Patient Satisfaction	Yip Telemedicine questionnaire ⁶²	Self	15 item	Participant			✓	
Aim 2: Potential effectiveness in improving weight, physical function and self-reported health						Timepoint			
Domain	Outcome/Co-Variate	Instrument	Adm	Length	Source	0	1	2	3
Participant Level Outcomes	Anthropometry	Weight/body mass index	CS	---	Participant	✓	✓	✓	✓
	Physical function	6 minute walk test (6MWT) ⁶³	CS	6 min	Participant	✓			✓
	Diet/Exercise Measures	REAP-S ⁶⁴ /IPAQ ⁶⁵	Self	16/7 items	Participant	✓			✓
	Subjective Health	PROMIS general health 10 ⁶⁶	Self	10 items	Participant	✓			✓
	Readiness to Change	URICA ⁶⁷	Self	12 item	Participant	✓	✓	✓	✓
Aim 3a: Ascertain the extent to which the intervention works on implementation outcomes						Timepoint			
Domain	Outcome/Co-Variate	Instrument	Adm	Length	Source	0	1	2	3
Adoption	Workflow adoption	Qualitative Interviews	RA	30 min	Staff				✓
	Staff adoption	Evidence-based practice adoption ⁶⁸	RA	12 item	Staff				✓

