- Qualitative Data: Thematic analysis⁷¹⁻⁷³ will be conducted by two researchers who will independently read transcripts, and conduct open coding⁷⁴. This enhances research rigor by allowing for different viewpoints⁷⁵. Through data immersion, focused coding using themes identified during open coding permits defined analyses⁷⁴. Codes will be derived *a priori* from interviews, and inductively derived from qualitative data, after which, the query tool will retrieve text by code, reviewed for content, relevance, and prevalence of themes.
- Statistical Analyses: Descriptive statistics (means, medians, proportions, 95% confidence intervals [CI]) will be computed for feasibility/acceptability. Telemedicine satisfaction will be assessed only at 12 week follow-up
- Sample Size Considerations: For the pilot, we estimation the proportion of patients attending and completing 10 of 12 scheduled sessions. If this proportion is 80%, then the half width of the expected 95%CI based on 30 enrolled patients is 14.3%, based on a normal approximation for binomial data.

Aim 2: Assess the potential effectiveness of an eHealth-delivered health coaching obesity intervention in improving weight, physical function and self-reported health in adults with obesity.

Objective & Subjective Participant-Level Outcomes:

- Weight & BMI: Weight will be measured using a Seca 770 analyzer (in clinic) and by the Omron HBF-514 (at home remotely). Target weight loss is defined by >5% of weight. BMI is calculated by Quetelet's formula⁷⁶.
- Physical function: *6-Minute Walk (6MWT)*⁶³ is a cardiovascular fitness surrogate measuring distance (normal 400-700m)^{77,78} related to function. A clinically important difference is 50-55m⁷⁹.
- Diet/Exercise: The Rapid Eating Assessment for Participants (REAPS)⁶⁴ is a 16 item survey (score 13-39) of diet habits. The 7-item international physical activity questionnaire (IPAQ) measures health-related activity⁶⁵.
- Subjective Health: The 10-question, non-proprietary *Patient Reported Outcomes Measurement Information Systems General Health-10 (PROMIS)*⁶⁶ captures physical, mental and social aspects of quality of life.
- Readiness to Change: The University of Rhode Island Change Assessment⁶⁷ is a 12 item questionnaire assessing one's stages of change based on contemplation, action, maintenance and pre-contemplation.

Data Analysis: Aim 2 will evaluate potential effectiveness of the intervention on patient outcomes:

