- Statistical Analyses: We will assess % weight loss and BMI change (primary outcomes), and change in the 6MWT, REAP-S, IPAQ, PROMIS and URICA (secondary outcomes). Linear/non-linear mixed effects models will evaluate weight, BMI and URICA change over time. To account for repeated measures and variation in trajectory over time, models will include random individual-level intercepts and time trends. A significant coefficient for the mean trend over time will indicate changes in outcomes. All data will be included as the models are robust to data missing at random under the assumptions of a linear mixed model. Paired t-tests will assess the change between baseline and follow-up in 6MWT, REAP-S, IPAQ and PROMIS.
- Sample Size Considerations: This pilot study intends to help develop future studies to evaluate recruitment, feasibility, acceptability and outcomes. Given the longitudinal nature of the data, a key parameter driving the future design is the intraclass correlation coefficient (ICC), a measure of dependence between observations taken on the same person. With 30 participants and a mean of 10 observations/person, we should be able to distinguish between a fairly low ICC of 0.15 versus an alternative of 0.34, based on a one-sample hypothesis test with a significance level of 0.05 and a power of 90%⁸⁰. For the primary outcome of % weight loss, using

a SD of 10.1%, the 95% CI would have half width of 3.6% based on our sample of 30, assuming a normal distribution.

Aim 3: Ascertain the extent to which the intervention works within an existing specialty obesity clinic on implementation outcomes such as workflow adoption, organizational change and compatibility.

Objective and Subjective Adoption, Implementation and Compatibility-Level Outcomes:

- Adoption Domain: *Workflow Adoption*: Questions using semi-structured interviews (methods per Aim 1) from the staff's experience with the intervention (whether it enhances/interferes with workflow; sustainability; technical or other difficulties in delivering care) will be explored. *Staff Adoption*: Haug's 12-item *Measure of Evidence-Based Practice Adoption*⁶⁸ assesses stage of change, experience, attitudes, organization barriers and strategies to support evidence-based practices (1-5 point scale - strongly disagree to agree).

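### The 90% power claim for the ICC assumes 10 observations per person; the documented schedule gives 4, at which one-sided power is about 61–63%

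*Combined protocol and SAP*

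**What the plan says.** Under Aim 2, Sample Size Considerations, the plan presents the ICC as central to designing the later trial and says: "With 30 participants and a mean of 10 observations/person, we should be able to distinguish between a fairly low ICC of 0.15", the alternative being 0.34. The calculation is described as "based on a one-sample hypothesis test with a significance level of 0.05 and a power of 90"%. Neither the sidedness nor the outcome concerned is given.

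The rest of the document describes the data as follows:

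- **Approach, Study Design:** a "12-week pilot that includes monthly assessments".
- **Table 1, Aim 2 rows:** the row "Weight/body mass index" is ticked at timepoints 0, 1, 2 and 3 and is administered by clinical staff. URICA is ticked at the same four. The 6-minute walk, REAP-S/IPAQ and PROMIS are ticked only at 0 and 3.
- **Aim 2, Statistical Analyses:** "mixed effects models will evaluate weight, BMI and URICA change over time".
- **Aim 2, Weight & BMI:** "Weight will be measured using a Seca 770 analyzer (in clinic) and by the Omron HBF-514 (at home remotely". No frequency is given for the home readings, and Table 1 has no row for them.
- **Aim 1, Sample Size Considerations:** the only other per-person count of 10 is "attending and completing 10 of 12 scheduled sessions", which counts coaching sessions, not outcome measurements.

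**The concern.** The number of observations per person drives the power of an ICC test. The claim uses 10, whereas no outcome in Table 1 has more than 4 scheduled timepoints. Describing 10 as a mean does not help: missed visits can only pull an average below the scheduled 4. Coaching sessions are weekly, but nothing in the plan says an outcome is recorded at them.

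One stated purpose of the pilot is to supply estimates good enough to design an evaluative trial (hypothesis H2), and the closing section on the proposed R01 says the results will feed its sample size calculation. A reader cannot tell whether the 90% describes the data that will be collected. If it does not, the pilot's ability to pin down a low ICC is overstated.

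**Working it through.** **Inputs.** From Aim 2, Sample Size Considerations: k = 30 participants, null ICC ρ0 = 0.15, alternative ρ1 = 0.34, α = 0.05. Observations per person: m = 10 (the plan's figure) or m = 4 (Table 1 and the monthly schedule).

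**Method.** One-sample ICC test in a one-way random-effects model. Let θ = ρ/(1−ρ) and C = (1 + mθ0)/(1 + mθ1).

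- Log approximation: power = Φ( √[(k−1)(m−1)(ln C)² / (2m)] − z_α ).
- Exact (one-sided): power = P( F > C·F₀.₉₅ ), with k−1 and k(m−1) degrees of freedom.

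Here θ0 = 0.15/0.85 = 0.1765 and θ1 = 0.34/0.66 = 0.5152.

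**The plan's own figure, m = 10.** C = 2.765/6.152 = 0.4494 and ln C = −0.800. The root term is √(29 × 9 × 0.6396/20) = 2.889.

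- One-sided: Φ(2.889 − 1.645) = 89.3%; exact F 89.5%. This reproduces the stated 90%.
- Two-sided: Φ(2.889 − 1.960) = 82.4%; exact F 84.1%. This does not.

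The plan's arithmetic is therefore right for its own input, as a one-sided test.

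**The documented schedule, m = 4.** C = 1.706/3.061 = 0.5574 and ln C = −0.5845. The root term is √(29 × 3 × 0.3417/8) = 1.928.

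- One-sided: Φ(1.928 − 1.645) = 61.1%; exact F 63.1%. Simulation of 100,000 trials agrees with the exact value to within 0.2 percentage points.
- Two-sided: Φ(1.928 − 1.960) = 48.7%; exact F 51.9%.

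**Between the two (one-sided):**

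| Observations per person | Log approximation | Exact F |
|---|---|---|
| 4 | 61.1% | 63.1% |
| 5 | 70.6% | 72.3% |
| 6 | 77.1% | 78.5% |
| 7 | 81.7% | 82.7% |
| 8 | 85.0% | 85.7% |
| 10 | 89.3% | 89.5% |

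**What 4 observations can deliver.** With 30 participants, 90% power is reached for an alternative ICC of 0.44 one-sided, or about 0.47 two-sided. Keeping 0.34 as the alternative at 90% one-sided power would need k = 1 + 2(1.645 + 1.282)² × 4/(0.3417 × 3) ≈ 68 participants.

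**Precision of the estimate.** The plan gives no expected ICC, so a range is shown. Approximate 95% half-width = 1.96 √{ 2(1−ρ)²[1 + (m−1)ρ]² / [m(m−1)(k−1)] }, with k = 30:

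| ICC | m = 4 | m = 10 |
|---|---|---|
| 0.34 | 0.198 | 0.145 |
| 0.70 | 0.138 | 0.119 |
| 0.90 | 0.055 | 0.049 |

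The loss is material at low ICCs, where the plan placed its contrast, and small at high ones.

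**The case against.** The strongest reply is that the documents do not cap observations at 4. The Table 1 ticks for weight are staff-administered measurements, and the plan separately provides a home scale. A mean of 10 suggests a count that varies between people, which fits home readings over a programme of 12 weekly sessions better than four fixed visits. If home weights were taken about weekly and analysed, 10 would be reached for weight and BMI and the 90% would stand. This is plausible and has to be allowed for. It remains inference, because no frequency is stated and no weight is tied to a session. It also cannot help URICA, which has the same kind of longitudinal model and stays at 4. URICA is a secondary outcome and the ICC sentence names no outcome, so that part carries less weight.

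Second, the wording of the test reads as directional, so the missing sidedness is a clarification rather than an error. That is fair.

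Third, the consequence is small. No decision rule uses this test, and the 3.6% half-width for percentage weight loss does not depend on the number of observations. If the true ICC is high, 4 observations suffice: one-sided power is about 97% at 0.5 and above 99% at 0.6. This stands, and it limits the seriousness of the point.

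Fourth, the 61–63% is itself favourable. It assumes that all 30 people contribute fully, and it rests on a one-way model although the plan specifies random intercepts and time trends. If only 24 contributed (20% dropout, taken here as a sensitivity case), one-sided power would be 53–55% at 4 observations and 82–83% at 10. The plan's own 90% makes the same assumption of 30 complete participants, so the comparison between 4 and 10 is like for like.

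**Conclusion.** The concern holds. The stated 90% rests on an input that the documented schedule does not supply. On that schedule of 4 observations, the same test has 61–63% power one-sided and 49–52% two-sided.

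The lower figures are conditional on only the Table 1 timepoints entering the analysis. For weight and BMI, about 10 analysed readings per person would restore roughly 90% one-sided; for URICA they would not. All figures assume 30 contributing participants and a one-way random-effects model. The finding bears on what the pilot may claim about the ICC, not on its sample size or primary analysis. It should be fixed because informing the next trial is a declared aim.

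**What to change.** State which observations enter the ICC and for which outcome, how often they are taken, and that α = 0.05 is one-sided. Then use whichever statement matches the intention.

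If only the Table 1 timepoints are analysed:

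> Thirty participants with 4 observations each give about 62% power (one-sided α = 0.05) to distinguish an ICC of 0.15 from 0.34, and 90% power to distinguish 0.15 from 0.44.

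If home weights are also analysed, add a Table 1 row giving their frequency and write:

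> For weight and BMI, 30 participants averaging 10 observations each give about 90% power (one-sided α = 0.05) to distinguish an ICC of 0.15 from 0.34. For URICA, with 4 observations, power is about 62%.

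Either version should add that the figures assume all 30 participants contribute. The cost is wording, one table row in the second case, and a less favourable stated power in the first. Enrolment and visits do not change.

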Aim 3: Ascertain the extent to which the intervention works within an existing specialty obesity clinic on implementation outcomes such as workflow adoption, organizational change and compatibility.

H3: Implementation will be adopted into the workflow (qualitative interviews and Haug's measure), lead to organizational change (General Organizational Index) and be perceived as having value (Willingness to Pay).

A transdisciplinary team will execute a pilot study for conducting a Type 2 hybrid effectiveness-implementation design²⁶ of this T3/T4 intervention. Expected outcomes include its feasibility and acceptability, the value added to specialized obesity care by improving outcomes, and the potential for eHealth integration into practice. The pilot builds logically to an R01 grant addressing critical gaps in pragmatic obesity strategies to improve health and care delivery pathways to with limited access to specialty care for long-term weight loss.

SIGNIFICANCE

Standard obesity advice within primary care is often ineffective in the long-term^{27,28}, which can amplify the morbidity observed in this population. The need to refer to specialty obesity care is needed⁶, yet access to care is lacking, especially in rural areas²⁴. Most evidence-based practices require busy clinicians to add visits²⁹ for direct, in-person IBT. These pathways are impractical due to workforce shortages, time constraints, and caseloads^{30,31}. Health coaches can assist in mitigating such challenges by effectively delivering IBT at higher

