b) **Health coaching:** In the DH-WWC Healthy Lifestyle Program, a health-coach led program plays an integral role in assisting with patient tracking, data gathering, self-monitoring, facilitating educational sessions and connecting patients and families with local resources. Coaches are trained in avoiding weight bias and, undergo specific motivational interviewing training, use shared decision-making, and reframe obesity as a chronic disease. They complete select wellness coaching programs, pass certification exams and serve as the program anchor, facilitating care coordination, executing treatment plans and setting SMART goals (specific, measurable, agreed upon, realistic, time-based). Content is based on national guidelines⁶.

c) **Telehealth:** Weekly coaching sessions will be conducted by video-conferencing in lieu of in-person visits. [name] telehealth team will configure an Android tablet (using the HIPAA compliant software, Vidyo⁶¹) to the subject's home intranet remotely, and will provide training to both patients and staff. The interface has easy access using simple taps. The coach's computer will have similar software. Added coaching support is offered ad-hoc, as in usual care, using on-demand connectivity. Subjects will be located in their homes.

d) **Messaging:** Currently, coaches send messages via the Epic integrated EHR patient portal, used in >40% of US medical centers. 'Push' message notifications to the tablet's face screen are received indicating a message is waiting for review. Within 48 hours, coaches are notified if messages are read, and if not, the coach can contact the patient by phone. Communication is confidential, documented, and tracked.

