Implementation	Organizational Change	General Organizational Inventory ⁶⁹	RA	12 item	Staff				✓
Compatibility	Patient Perception of Value	Willingness to Pay ⁷⁰	Self	2 item	Participant	✓			✓

ADM- Administration; CS – clinical staff; IPAQ – International Physical Activity Questionnaire; PROMIS: Patient Reported Outcome Measures Information Systems; RA: research assistant; REAP-S: Rapid Eating Assessment for Participants – Shortened Version; 6MWT: 6-minute walk test; URICA: University of Rhode Island Change Assessment: Short Form for Physical Health Behavior State.

Aim 1: Evaluate the feasibility and acceptability of an eHealth-delivered (remote monitoring and video-conferencing) health coaching obesity intervention in a rural, academic, specialty obesity clinic.

Feasibility: The following rates will be computed: screened for inclusion ($\# \text{ screened} \div \# \text{ potentially eligible}$); eligibility [$\# \text{ screen positive} \div \# \text{ screened for inclusion}$]; enrollment [$\# \text{ enrolled} \div (\# \text{ screen positive} \& \text{ eligible})$]; completion ($\# \text{ completing sessions} \div \# \text{ enrolled}$); assessment ($\# \text{ completing all assessments} \div \# \text{ enrolled}$). We will assess entry criteria (reasons for dropout/non-adherence) and time to collect data. Enrollment success will be defined as 30 patients. Adequate retention is defined as a dropout rate of <20%. Completion of >80% of post-study measures will be defined as adequate. Attending >80% of sessions will be considered acceptable. Staff will track equipment, software or technical issues (malfunctions, data loss, hardware) in a journal.

Acceptability: Qualitative interviews will ensure the appropriateness of the pilot and its strengths/weaknesses. The RA will conduct, record, and transcribe each 30min interview. Field notes, questions, and themes outlining the content/context allows for codebook development, tailoring it to the subject's needs in the future. Topics include: feasibility, acceptability; missing features; telehealth's impact (including sound/video quality); Amulet's usability and perceived barriers to use; complexity and flaws; strategies for improving compliance; feedback. Quantitative data will be measured using the 15-item, 5-point scale (*Telemedicine satisfaction questionnaire*⁶²).

Data Analysis: The analysis of Aim 1 is primarily descriptive. Data will be analyzed as follows:

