- Implementation Level: *Organizational Change*: General Organizational Index (GOI)⁶⁹ is an interview of 11 domains with a 5-point rating of: program philosophy, commitment, client eligibility and identification, health promotion plan and its treatment, training, process and outcome monitoring, assessment, quality assurance, choice supervision, & penetration. It has reliable inter-rater agreement and internal consistency.
- Compatibility: *Patient Perception of Value*: Two questions will assess *Willingness to Pay (WTP)*⁷⁰ – whether they would pay for telemedicine delivery of the intervention in lieu of in-person travel time or cost.

Data Analysis: We will use mixed-methods to analyze data from Aim 3 as follows:

- Qualitative Data: Interview data will be managed and analyzed using *Dedoose* as described in Aim 1.
- Statistical Analyses: Descriptive statistics (means, medians, 95% CI) for adoption, organizational change will be assessed at follow-up only. Changes in WTP will be estimated using a paired 2-sample t-test.
- Sample Size Considerations: For changes from baseline on WTP, there will be 80% power to detect large differences in change from 0.32 to 0.28 times a SD assuming a range of within-person correlations (0.2-0.4).

Data Management: Our team is experienced in pilot delivery, data management/acquisition, and validation procedures including: a) health coach training; b) continuous feedback; and c) final data editing. The PI and co-l's will meet staff regularly, supervise and identify quality control issues early to address them promptly. Non-HER entered measures will be collected by the RA using REDCap⁸¹, a secure web/tablet based data collection tool. The Analytics Institute manages a DH-WWC patient registry who will facilitate data extraction. Interviews will be recorded in duplicate using a digital tape recorder. Records will be kept in a locked cabinet. Identifiers will be assigned at enrollment and kept behind the D-H firewall, with a password protected linked file. Data will be exported to *Dedoose* and *R* for analysis with complete labeling intact (variables, labels, missing values)

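### H3 predicts organizational change on the General Organizational Index, but the index is taken once, at follow-up, so the plan yields a level and cannot evaluate that component of H3

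*Combined protocol and SAP*

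**What the plan says.** In Specific Aims, H3 predicts that implementation will be taken up in the workflow, will "lead to organizational change (General Organizational Index"), and will be seen as having value. Each outcome has its own measure: interviews and an adoption scale for the first, the index for the second, willingness to pay for the third.

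Table 1 labels its Implementation row as organizational change, names the instrument "General Organizational Inventory" with 12 items and staff as the source, and ticks timepoint 3 alone. The Aim 3 text calls it an Index and describes an interview of 11 domains on a 5-point rating. The Aim 3 Statistical Analyses paragraph reads: "Descriptive statistics (means, medians, 95% CI) for adoption, organizational change will be assessed at follow-up only".

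Willingness to pay, in the same aim, is treated differently. Table 1 ticks "Willingness to Pay" at timepoints 0 and 3, and the analysis says "Changes in WTP will be estimated using a paired 2-sample t-test".

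The Study Design paragraph describes a single-arm study recruiting from one clinic.

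**The concern.** A claim of change needs a second measurement or some other reference against which the follow-up value can be read. The plan provides neither for the index. Followed exactly, it reports a follow-up mean under the label of organizational change, which leaves that part of H3 unanswered and invites a level to be read as an effect of the intervention.

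The setting adds to the risk. The clinic was not starting from nothing. Within its Healthy Lifestyle Program, "a health-coach led program plays an integral role in assisting with patient tracking, data gathering, self-monitoring" and related tasks; the coach is supervised by the clinician; and Potential Problems/Alternative Strategies describes everything apart from video-conferencing and eHealth as standard care. A favorable rating at follow-up might in part describe the clinic as it already was.

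**Working it through.** The plan gives no sample size, standard deviation, target score or number of staff raters for the index, so there is no figure to reproduce. The check has four steps.

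**1. Timing of the Aim 3 measures (Table 1)**

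| Measure | Source | Timepoints | Does H3 claim a change on it? |
|---|---|---|---|
| Staff interviews | Staff | 3 | No (adoption) |
| "Evidence-based practice adoption" scale | Staff | 3 | No (adoption) |
| General Organizational Index/Inventory | Staff | 3 | Yes |
| Willingness to pay | Participant | 0, 3 | No (perceived value), but analyzed as a change |

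The index is the only measure to which H3 attaches a change, and it has no baseline. Table 1 and the analysis text agree on this, so it is not an artefact of a broken table.

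**2. What the data can estimate**

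Let F be the follow-up mean and B the mean before the program. The change is D = F - B. The plan observes F. It does not observe B and gives no substitute for it: no comparison clinic, historical score or threshold. It yields no pre-post pairs on the index, however many staff are rated.

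**3. How much F alone says about D**

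Assume each rating runs from 1 to 5; the text says only that it is a 5-point rating. B then lies between 1 and 5, so D lies between F - 5 and F - 1.

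| Follow-up mean F | Lowest D (F - 5) | Highest D (F - 1) |
|---|---|---|
| 3 | -2 | +2 |
| 4 | -1 | +3 |
| 4.5 | -0.5 | +3.5 |
| 5 | 0 | +4 |

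The interval is always 4 points wide, the full range of the scale. Only a mean at the ceiling rules out a decline, and even that allows no change at all. A 95% confidence interval around F expresses uncertainty about the level and does nothing to narrow B.

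**4. Whether a baseline could be fitted in**

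The Study Timeline puts staff training and site preparation in month 1, recruitment from month 2 and the intervention row from month 3. Training, and client eligibility and identification, are both among the rated domains. Month-1 training and month-2 screening could each affect a rating, so the clean window is month 1, ahead of staff training.

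**The case against.** The strongest reply is that the index may rate the new program and not the clinic. The domain list includes program philosophy and penetration, and the title of the paper cited for the index (reference 69) refers to program fidelity. If so, no score may exist before the program starts, a single follow-up rating is reasonable, and the fault shrinks to the word change. The documents do not settle which unit is rated. This limits the argument about existing practice and bears on the choice of fix. It does not rescue H3, because under either reading the reported figure is not a change.

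A second reply is that this is a 30-patient pilot with a descriptive analysis and an openly stated single timepoint. That is fair, and it lowers the severity. A descriptive statement of change still needs something to compare with.

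Several stronger readings are tempting but unsupported:

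- *Nothing in Aim 3 speaks to change.* Staff interviews ask whether the intervention helps or hinders workflow, and the adoption scale "assesses stage of change, experience, attitudes, organization barriers and strategies to support evidence-based practices". The interviews may give retrospective, qualitative views of change. Neither source gives a change in the index, which is the measure H3 names.
- *All the staff measures lack a baseline they need.* H3 claims no change on the interviews or the adoption scale, and experience with an intervention cannot be asked about beforehand. Only the index matters here.
- *Particular rated domains were already in place, so the score will be inflated.* The domains are named but not defined. The list as printed has 10 comma-separated entries against a stated 11, so even its boundaries are uncertain. The new telehealth training for staff also means that the training domain is not purely pre-existing. No domain-by-domain match or size of bias can be shown.
- *The later trial's design is compromised.* The R01 section gives the index no role in sample size calculations.

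**Conclusion.** The point stands in a limited form. One of H3's three outcomes cannot be evaluated from the measure H3 assigns to it, because that measure is taken once with no reference value. This rests on the agreement of H3, Table 1 and the analysis text, and needs no assumption about scoring. The numerical bounds do assume a 1-to-5 rating.

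That a high level could partly reflect existing practice is conditional: it applies if the index is rated for the clinic, and its size is unknown. A reader might infer that the result will be biased upward, but the documents do not show this.

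Severity is low to moderate. Aims 1 and 2 are unaffected.

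**What to change.** First state what the index rates, the clinic or the new program, and reconcile the two descriptions of the instrument (Index with 11 domains; Inventory with 12 items) into one version.

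- **If it can be rated before the program starts:** add a timepoint-0 administration of that version to the same staff in month 1, ahead of staff training and before recruitment opens in month 2. Tick it in Table 1 and amend the analysis sentence. Report the pre-post difference descriptively, with the number of raters and no causal attribution.
- **If it cannot, or if the program has already begun:** restate H3, Aim 3 and the outcome label in Table 1 and the Aim 3 text as organizational status at follow-up, and make no claim of change.

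The first option costs one extra short round of staff interviews, which must be fitted into month 1; the documents do not say when the research assistant starts. Even then, a difference within one clinic stays descriptive. The second costs only wording and a less ambitious H3.
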